1.0 Objectives / Specific Aims

Newborns who are born premature or suffer brain injury at birth are at risk for motor problems. The common motor skills of reaching and grasping that infants have to learn can be weaker on one side of the body, depending on the site of the brain injury. These skills are practiced with an occupational therapist, to help the infant strengthen these skills. The gold standard rehabilitation intervention to address one sided motor weakness is Constraint Induced Movement Therapy (CIMT). During CIMT interventions, an infant wears a removable splint or puppet on their stronger hand while the therapist engages the infant in various activities targeted to improve functioning of the weaker side. CIMT encourages infants to move the weaker arm and hand and strengthen the circuits in the brain involved with movement. Even with the high intensity therapy program of CIMT, it takes between 40-120 hours total treatment time for most infants to improve their motor skills. We hope to improve motor outcomes by pairing CIMT with technology shown to improve motor functioning due to brain damage.

The purpose of this study is to evaluate the safety and effectiveness of using Electromyography (EMG) muscle sensors to trigger a non-invasive brain stimulation technique, called Transcutaneous auricular Vagus Nerve Stimulation (taVNS) during CIMT in order to improve motor outcomes for this intensive rehabilitation intervention.

Explanation of technology:

- **Electromyography (EMG) Sensors:** EMG sensors are adhesive electrode sensors that detect electrical activity in a muscle, in other words sensors that detect if a muscle is “on or off”. In this study we will place EMG sensors over key muscles in the shoulders and trunk to automatically detect when an infant is reaching or using their trunk to work on activities like sitting or rolling in therapy. When muscles are activated, it will trigger taVNS stimulation. Pairing nerve stimulation with movement may boost rehabilitation outcomes when paired with motor activities in infants and adults post stroke or brain injury.

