to trigger stimulation. Placing EMG sensors over key muscles in the shoulders and trunk we allow us to automatically detect when an infant is reaching or using their trunk to work on activities like sitting or rolling. By using EMG sensors we should be able to pair stimulation with movements reducing the burden on the therapist and allowing them to focus on facilitating a high quality treatment session. Automating the stimulation would make taVNS-paired CIMT more achievable in the home-based CIMT programs. Home-based delivery of CIMT is considered best practice for pediatric clients so families can be fully engaged, burden for families is reduced, and new skills can easily transfer to the natural environment for better carry over of treatment.

Qualifications

We have a unique collaboration of experts in brain stimulation, pediatric brain injury, translational clinical science and pediatric occupational therapy in this pilot project, and we are one of the few groups able to rapidly translate this neuromodulatory modality into home-based CIMT services. Refining the treatment protocol for home-based taVNS+CIMT and trialing incorporation of reliable taVNS triggering by this device we will provide us strong data to submit a grant for a randomized trial of home delivered taVNS+ CIMT in infant hemiplegia.

Study Aims

Aim 1: Investigate the feasibility of incorporating automatic triggering of the taVNS device using EMG sensors. *Rationale:* Manual taVNS triggering is mentally taxing for a therapist providing intensive, CIMT intervention. Movement based triggering would decrease the mental effort for using taVNS allowing the therapist to focus more on the treatment session. *Aim specific methods:* We will systematically test key muscle groups to see if EMG can be used to trigger taVNS stimulation at least 75% of the total time for active infant arm and trunk movements during CIMT. The first 2 participants will be completed in clinic to allow for updates to EMG system real time. After the first 2 participants complete the study we will trial the EMG system in the home setting for Aim 2.

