perceptual level. If at any point during the treatment it seems as if the infant is perceiving the stimulation (reaching to ear, grimace, etc) a break is taken and then PT is retested to determine if stimulation level should be decreased. taVNS treatment is paired with suck-swallowing during 1 (n=15) or 2 (n=18) oral feeds/day, for 2-3 wks. Results: Efficacy outcomes: 19/35 (54%) infants destined for G-tube attained full oral feeds with taVNS-paired feeding in a mean of 2 weeks or less. We showed a dose response with twice vs once daily treatments in the increase of daily po feeding volumes ($F, 8.05, p=0.01$) & faster time to full po feeds ($p<0.05$). In secondary outcomes, diffusion kurtosis imaging before and after taVNS treatment, showed greater white matter plasticity changes in fractional anisotropy (FA) and white matter complexity for Responders versus Non-Responders in corpus callosum and external capsule, per week of development. Safety outcomes: We observed no bradycardia ($HR<80\text{bpm}$ 5sec), no skin irritation. Persistent increase in discomfort scores (NIPS >3) occurred in only 3/228 sessions (1.3%) resolving with decreasing current. In summary, our first-in-human neonate and infant pilot trial of taVNS paired with an oromotor task of bottle feeding, using our custom taVNS system, showed safety and feasibility, and achieved encouraging results in >50% of infants slated for G-tube achieving full oral feeds in 2 weeks.

C1.2 CIMT+taVNS Ongoing Safety & Feasibility Pilot

Pediatric CIMT trained therapists provided 40 hours of CIMT paired with taVNS treatment at $0.1\text{mA} < \text{Perceptual Threshold (PT)}$ over 4 consecutive weeks. Infant's motor abilities are tested prior to therapy start, immediately after the 4 weeks of therapy and again 3 months post treatment. Primary Outcome: QUEST- an assessment of quality of arm/hand movement in infants & children with CP.

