C2.2.2 Targeted Muscle Groups We aim to automate 75% of stimulation time without significantly increasing the burden of system set-up/treatment delivery. We will use 2 sets of EMG sensors placed on the muscle groups activated in the vast majority of reaching and dynamic balance tasks.

- Reaching- Immature reaching in infants is initially driven by the biceps and triceps^{28,29}. As targeted reaching improves there is an increased use of the deltoids and upper trapezius as prime movers. Depending on the age/ability of the child we will target biceps brachii or anterior deltoid^{28,29}.
- Trunk control- EMG literature related to development of dynamic sitting balance indicates that thoracic level paraspinal muscles are most involved with emerging sitting balance and transitions to lumbar paraspinal activation as infants progress to more independent sitting balance²⁸⁻³⁰.

C2.2.3 Outcome measures for EMG automation taVNS stimulation is most effective when directly paired with active movements. Infant movement kinematics are characteristic of continuous movements rather than discrete movements. Since motions are not clearly discrete, we cannot count the number of stimulations and movements. Instead, a second therapist will record the time that the infant is actively engaged in movement tasks and compare that to the total time of taVNS stimulation, recorded by data acquisition modules in our taVNS set-up. One therapist will be delivering CIMT, a second therapist will be recording active movement time. For the first 2 participants, treatments will be completed in the research lab. This will allow the full team to be present, making sure that EMG triggered stimulation is occurring at the same time as active movement (the screen turns green when stimulation is on). If stimulation is not being delivered during active movement, modifications will be made to the system (e.g. changing amplification threshold for triggering, adjusting sensor location, etc). If total stimulation time is within 75% of total active movement time for therapy sessions in the first 2 infants, then we will transition CIMT delivery to the home-based setting for the final 3 infants.

C2.1.2 Treatment Delivery: CIMT-trained therapist with assistance from a research assistant will deliver CIMT for 40 hours (2 hours/day, 5 days/week for 4 weeks) +taVNS delivered via the BabyStrong (BS) system, (Soterix taVNS electric pulse generator unit & Neolead® electrodes).

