4.0 Study Endpoints

Primary Research Question: Can taVNS stimulation be automatically triggered during 75% of the total time for active infant arm and trunk movements during CIMT? **Primary Outcome measure:** Percentage of treatment sessions where total stimulation time was 75% of total active movement time.

Limitations and alternative approaches: *Trialing EMG system:* We will trial the EMG sensor system first with two healthy infants in the CHP laboratory setting to trouble shoot set-up and connection issues. The BSL and CIMT team will make any necessary modifications to the EMG-taVNS set-up. *Comparing total movement time to total stimulation time does not ensure stimulation is being provided at the appropriate time:* The stimulation device changes color when stimulation is being provided. Therefore, a second 'recording' therapist can monitor if the screen is green('on') when also recording active movement.

Aim 2: To generate proof of concept evidence demonstrating ability to provide high fidelity CIMT+taVNS treatment in a home-based setting in 3 infants. We will have a second therapist videotape CIMT therapy sessions while the CIMT therapist is delivering taVNS in the home with EMG triggered taVNS. We will randomly score 20% of sessions for CIMT treatment fidelity with published CIMT Fidelity tool. This aim will be completed with the final 3 participants after EMG set-up is finalized with first 2 participants.

Secondary CIMT+taVNS feasibility outcomes: Ability of therapist to operate taVNS easily and successfully by earning a "meet or exceed" score (3 or 4) on random therapy sessions by CIMT Fidelity Instrument. Ability of infant to tolerate wired ear electrode while remaining securely in place during sessions.

Secondary CIMT +taVNS efficacy outcomes: Change in the functional motor outcomes pre and post intervention on the *Quality of Upper Extremity Skills Test (QUEST)*

Title: Extending taVNS Paired with Infant CIMT into a Home-Based Setting: Technology Development Requisite for a Randomized Trial

PI: [name]

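### The primary outcome and the lab-to-home rule compare two totals, so off-movement and manual stimulation can carry a session to 75% when automatic overlap is lower

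*Combined protocol and SAP*

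**What the plan says.** Aim 1 (section 1.0) is to see whether "EMG can be used to trigger taVNS stimulation at least 75% of the total time for active infant arm and trunk movements". Sections 3.0 and 10.0 describe the standard for moving to homes in similar terms. The primary research question in section 4.0 asks about automatic triggering while the infant is moving. All of these describe an overlap between EMG-triggered stimulation and movement.

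The outcome measure that follows in section 4.0 is a ratio of totals: "Percentage of treatment sessions where total stimulation time was 75% of total active movement time". Section 3.0 (C2.2.3) explains how the two totals arise: a second therapist is to "record the time that the infant is actively engaged in movement tasks and compare that to the total time of taVNS stimulation". Stimulation time comes from the device's data acquisition interface. Under Treatment Delivery, item 4, that interface covers both EMG and manual triggering; the manual button is kept for hand movements such as grasping. The same comparison of totals in the first two infants decides whether the last three are treated at home.

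On timing, section 4.0 lists as a limitation that totals do not show whether stimulation came at the right moment. Its remedy is that the recording therapist can watch the green screen while timing movement. In the lab the full team also watches for coincidence, and "If stimulation is not being delivered during active movement, modifications will be made to the system".

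**The concern.** The question is about overlap, but the outcome contains no overlap term. Two kinds of stimulation enter the numerator without answering the question.

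- **Stimulation outside recorded movement.** The trigger is muscle activity: "When muscles are activated, it will trigger taVNS stimulation". The arm and paraspinal muscles chosen can be active when the observer is not recording movement, and nothing in the formula removes that time.
- **Manual stimulation.** Minutes from the therapist's button count toward the 75%, although the aim is automatic triggering.

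The plan itself says why timing matters: "taVNS stimulation is most effective when directly paired with active movements". The ratio also governs the move into homes, and section 1.0 (Qualifications) says the data are meant to support a grant for a randomized trial. A system that fires too readily, or that relies on the button, could be taken forward as having met the automation target.

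**Working it through.** **Inputs from the plan.** Sessions last 2 hours (120 minutes), 5 days a week for 4 weeks. The plan's own dose figure reproduces: 2 × 5 × 4 = 40 hours. That is 20 sessions per infant, so 40 in the lab (2 infants) and 60 at home (3 infants). The threshold is read as at least 75%, as in Aim 1. Section 12.0 gives no power calculation for the primary outcome, so there is no further figure to reproduce.

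**Inputs assumed, because the plan does not give them.** M is active movement minutes in a session and N = 120 − M is the rest. c is the share of M with stimulation on. q is the share of N with stimulation on.

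**Formula.** The plan's ratio is (cM + qN)/M = c + qN/M, while the overlap is c. The ratio reaches 0.75 when off-movement stimulation totals (0.75 − c)M minutes, that is, when q = (0.75 − c)M/N.

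Off-movement stimulation that lifts a session to 75%:

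| True overlap c | M = 30 (N = 90) | M = 60 (N = 60) | M = 90 (N = 30) |
|---|---|---|---|
| 50% | 7.5 min (8.3%) | 15 min (25%) | 22.5 min (75%) |
| 60% | 4.5 min (5%) | 9 min (15%) | 13.5 min (45%) |
| 70% | 1.5 min (1.7%) | 3 min (5%) | 4.5 min (15%) |

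The ratio has no ceiling. With M = 40, c = 60% and q = 25%, it is (24 + 20)/40 = 110%, while overlap is 60%.

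**Manual stimulation alone.** Take M = 60, with EMG covering 36 minutes (60%) and the button covering another 9 minutes of movement. The ratio is (36 + 9)/60 = 75%, with nothing off-movement, but automatic overlap is 60%.

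**On the scale of the primary outcome.** Suppose session overlap is Normal with mean 70% and SD 10 points, M = 60, and q is the same in every session. The share of sessions scored as reaching 75% is P(c + q ≥ 0.75):

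- q = 0: 31%, the true share
- q = 5%: 50%
- q = 10%: 69%
- q = 20%: 93%

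**The case against.** The strongest reply is that the plan already sees the problem. Section 4.0 names the limitation almost exactly, the recorder can check the screen, and in the lab the full team watches timing and adjusts trigger threshold and sensor position. Those adjustments would change later sessions' totals. Sections 3.0 and 10.0 also word the home standard as accurate triggering during movement. So the issue was not overlooked, and the set-up may end up well timed. But the checks are not part of the calculation. The screen check is made while movement is being recorded, and the written lab action concerns stimulation missing during movement. Neither takes off-movement or manual minutes out of the outcome or the rule.

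Second, every magnitude above is assumed. This is correct. With 90 active minutes the distortion is much weaker: a 50% overlap would need stimulation for 75% of the remaining time to pass. The 93% figure depends on a high off-movement rate that is unrelated to overlap.

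Third, overlap is harder to measure than totals. Section 3.0 stresses that infant movement is continuous, and observers mark starts and stops late. As an assumed illustration, 10-second bouts recorded 1 second late lose 10% of overlap, so a true 80% reads 72% (0.80 × 0.90) and fails, while totals are unaffected. This stands, and it is why the fix includes a timing tolerance and keeps the plan's ratio in view.

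Fourth, this is an uncontrolled pilot of up to five infants with no test specified on the primary outcome. That limits the consequence to a descriptive percentage and a go/no-go decision, but those are what the pilot is for.

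**Conclusion.** The point holds. The outcome in section 4.0 and the lab-to-home rule in section 3.0 do not measure what the primary question asks. Off-movement and manual stimulation both count toward 75%, so a session can be scored a success when automatic overlap is below it. The mismatch follows from the text alone. Its size depends on active minutes, off-movement firing and button use, none of which the plan gives. At 60 active minutes of 120, 9 off-movement or manual minutes are enough to turn 60% into 75%.

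A reader might go further and infer that the results will be inflated. The documents do not show that; they show only that the formula cannot detect it.

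A reader might also infer a safety gap: section 10.0 lists fidgeting as a discomfort sign, fidgeting might itself fire the trigger, and only a current decrease is written there. The documents do not support calling this an error. Section 10.0 ties its response to the feeding trial, and section 8.0 describes the feeding pilots' procedures as similar. In the feeding trial, according to section 2.0, if "it seems as if the infant is perceiving the stimulation (reaching to ear, grimace, etc) a break is taken and then PT is retested". That supports carrying the break over, although none of these sections mentions the EMG trigger. The effect on the ratio is also ambiguous. If 10 minutes of fidgeting are recorded as movement in a session with 40 of 60 minutes covered (67%), the ratio becomes (40 + 10)/70 = 71% if all of it triggers, or (40 + 5)/70 = 64% if half does. At most, a written pause is a missing detail.

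**What to change.** For both the primary outcome and the lab-to-home rule, define the numerator as EMG-triggered stimulation time that overlaps recorded active arm or trunk movement. Take it from time-stamped device and observer records, and state in advance a small timing tolerance for observer lag. Use the same definition of active movement in the denominator, and say whether hand-only movement, which the manual button serves, belongs there.

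Report three things beside it: manual stimulation time, stimulation outside active movement, and the plan's ratio of totals.

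If the device log cannot be time-stamped, score overlap from the session video already planned, with the device screen in view, in a random 20% of sessions: 8 of 40 in the lab and 12 of 60 at home. Section 4.0 already plans a 20% fidelity sample at home. The screen is described only as showing that stimulation is on, so the trigger source would still have to come from the log.

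The cost is protocol wording and some work to align the two records; item 4 of Treatment Delivery promises only amounts of stimulation time and intensity. With the same denominator, the new figure can only equal or fall below the plan's ratio. Part of any drop may be observer timing error rather than poor triggering, which is a reason to show both.

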- 1) Hydrogel electrodes are placed in front of tragus and inner tragus/cymba chonchae, securing the wires behind head with tape. taVNS unit is attached to the baby using Velcro cummerbund (Fig.1, 2).

Title: Extending taVNS Paired with Infant CIMT into a Home-Based Setting: Technology Development Requisite for a Randomized Trial

PI: [name]

- 2) EMG electrodes will be placed on the shoulder (biceps/deltoid m) and on the trunk (paraspinus m) and connected to the taVNS unit via a wired interface.
- 3) CIMT and BSL therapists establish perceptual threshold (PT) daily, increasing slowly, until infant shows signs of tingling sensation. TaVNS is delivered at $0.1\text{mA} < \text{PT}$, $500\mu\text{sec}$, 25Hz, during each CIMT session, timed with movements of the weaker arm /trunk.
- 4) A CIMT therapist will deliver CIMT and use the manual trigger if needed for hand movements, while a second 'recording' therapist will record the active movement time. The Data Acquisition (DAQ) interface will record the amount of stimulation time and intensity from both EMG and manual triggering.
- 5) Good, moderate or poor impedance is constantly displayed on the taVNS unit. With poor contact, a beep sounds, and the electrode is adjusted.
- 6) Parent and OT will answer weekly questionnaire to assess their perception of ease of use, infant tolerance, and any recommendations for improvement of taVNS system or delivery.

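### The therapist who times active movement, the denominator of the primary outcome, may watch the stimulation display while timing, and neither a second timing nor a recorded measure of overlap is planned

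*Combined protocol and SAP*

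**What the plan says.** - **Outcome and decision.** Section 4.0 counts the sessions in which total stimulation time was 75% of total active movement time. C2.2.3 uses the same ratio to decide whether delivery moves to the home: "If total stimulation time is within 75% of total active movement time for therapy sessions in the first 2 infants".
- **Numerator.** C2.1.2, item 4: "The Data Acquisition (DAQ) interface will record the amount of stimulation time and intensity from both EMG and manual triggering".
- **Denominator.** C2.2.3: "One therapist will be delivering CIMT, a second therapist will be recording active movement time". C2.1.2, item 4, repeats this: "while a second 'recording' therapist will record the active movement time". The judgement is not a simple one, because C2.2.3 also says: "Since motions are not clearly discrete, we cannot count the number of stimulations and movements".
- **Display.** Section 4.0 says that the stimulation device changes colour when it is on. C2.1.2, item 1, places it on the infant: "taVNS unit is attached to the baby using Velcro cummerbund". Section 4.0 concedes that comparing totals does not show that stimulation came at the right time, and offers this in answer: "a second 'recording' therapist can monitor if the screen is green('on') when also recording active movement".
- **Lab check.** For the first 2 infants, C2.2.3 says of the lab setting: "This will allow the full team to be present, making sure that EMG triggered stimulation is occurring at the same time as active movement".
- **Video.** Section 10.0 gives its purpose as measuring CIMT fidelity. Aim 2 scores 20% of sessions with the fidelity instrument, in the final 3 infants.
- **Staffing.** C2.1.2 mentions a research assistant. Section 4.0, Aim 2, has a second therapist film at home. Sections 6.0 & 7.0 have a second team member assist, film and monitor. Section 13.0 says that the PI or a co-investigator attends patient visits.

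**The concern.** Movement time is the reference against which the EMG trigger is judged, so it should be obtained independently of the trigger's output. Here one person makes a live judgement about movements without clear boundaries, and may have in view a coloured signal showing when the system believes movement is occurring. A timer who is unsure whether a movement has begun or ended could, without intending to, settle the question by the screen.

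At stake are the classification of each session and the decision to move to the home. The text available for review plans no second timing of movement, no written definition of active movement, and no recorded measure of overlap between movement and stimulation. The screen check is the plan's answer to the overlap problem, but no data from it are described. The conceded gap therefore stays open while the independence of the denominator is put in doubt.

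**Working it through.** The plan gives no error rate, agreement figure or power calculation for this outcome, so there is no figure to reproduce. Three short derivations show what follows.

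**Direction of cueing.** Let S be stimulation time, D true movement time and r = S/D. If the display pulls the recorded time a fraction k of the way from D to S (k above 0, at most 1), then

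recorded D = D + k(S − D), and recorded ratio = r / (1 − k(1 − r)).

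For r below 1 the divisor is below 1, so the recorded ratio exceeds r and approaches 1 as k rises. The documents give no value for k.

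**Sensitivity of the 75% threshold to any error in D.** Section 4.0 says that the ratio was 75% and C2.2.3 says within 75%; I read both as at least 0.75. If a share d of movement time is missed, the recorded ratio is r/(1 − d), which reaches 0.75 at d = 1 − r/0.75.

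| True ratio | d needed | With an assumed 60 min of movement | Assumed 30 to 90 min |
|---|---|---|---|
| 0.70 | 1 − 0.70/0.75 = 6.7% | 4 min missed: 42/56 = 0.75 | 2 to 6 min |
| 0.65 | 1 − 0.65/0.75 = 13.3% | 8 min missed: 39/52 = 0.75 | 4 to 12 min |

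Movement time per 2-hour session is not stated, hence the range. Over-recording works the other way: a true 0.80 falls to 0.75 when movement is over-recorded by 0.80/0.75 − 1 = 6.7%.

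**Totals against overlap.** Let F be stimulation delivered outside movement. The share of movement time that was stimulated is (S − F)/D = r − F/D. It never exceeds the ratio of totals, and equals it only when F = 0. The primary research question asks about stimulation during movement, so this share answers it more directly.

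**Scale.** At 5 sessions a week for 4 weeks, each infant has 20 sessions: 2 × 20 = 40 in the lab and 3 × 20 = 60 at home. The 20% fidelity sample at home is 0.20 × 60 = 12 sessions.

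**The case against.** The strongest reply is that section 4.0 only permits the recording therapist to look at the screen. The delivery steps in C2.1.2 give that person movement timing and nothing else. This stands: a reader might infer that the timer must watch the display, and the text does not say so.

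Second, the 6.7% and 13.3% margins cover movement missed for any reason and would apply equally to a masked timer. That also stands. They show how sensitive the threshold is, not how much cueing occurs or what masking would gain.

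Third, hiding the display from the timer at home could remove the plan's own check on timing, and C2.1.2 and section 13.0 leave unclear who else attends. This is a fair limit on the remedy, and mandatory shielding at home is not justified.

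Fourth, the full team is present in the lab. Their role is to see that stimulation coincides with movement and to adjust the system. That is tuning; it neither masks the timer nor measures movement time a second time.

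Finally, this is an uncontrolled pilot of up to 5 infants with no powered test. That limits the weight of the point but does not remove it, since this ratio is the pilot's primary outcome.

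**Conclusion.** The concern holds in limited form. The plan lets one person both judge the reference measure and see the output being tested, and plans no second timing or recorded overlap. If cueing occurred, it would favour success for sessions truly below 75%. Its size is unknown. The margins above rest on reading success as at least 0.75 and on assumed minutes of movement.

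Two stronger conclusions are tempting. One is that the success rate will be inflated: the documents do not show that cueing will happen, and other timing errors can act in either direction. The other is that nobody will time movement at home: C2.2.3 and C2.1.2 assign timing in general terms, and the home descriptions omit it without saying that their task lists are complete. That text needs reconciling, but it does not show that the measurement is missing. The point is worth acting on because the main correction costs little. Confidence is medium, as parts of the document were not available for review.

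**What to change.** 1. In 4.0 and C2.1.2, state that the recording therapist logs movement start and stop times and does not use the stimulation display to do so. In the lab, other team members already present do the green-screen check, for tuning only. At home, give that check to another study person if one attends. Otherwise keep it with the timer and report as a limitation that the timer was not masked. Physical shielding at home is not required.
2. Confirm whether the DAQ record is time-stamped; C2.1.2 mentions only amount and intensity. If it is, report the share of logged movement time that was stimulated beside the ratio of totals. If not, state the limitation. This depends on item 1, because a cued movement log would distort the overlap too.
3. Optionally, have existing staff re-time short segments of the videos already drawn for fidelity scoring, using a written definition of active movement, and report the difference from the live record.
4. Reconcile C2.2.3 and C2.1.2 with 4.0 (Aim 2), 6.0 & 7.0 and 13.0 on who times movement at home.

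**Cost.** Clock alignment between the movement log and the DAQ, and a few hours of staff time. With assumed 30-minute segments, item 3 needs 12 × 0.5 = 6 h for one viewing. The reported success rate may fall. No treatment changes.
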